## **Rationale/Background:**

### **BACKGROUND AND SIGNIFICANCE**

The American Cancer Society's most recent estimates regarding bladder cancer in the United States are that there will be 74,690 new cases with 15,580 deaths in 2014. The chance of a man having this cancer is about 1 in 26. For women, it is 1 in 87. In men, bladder cancer is the fourth most common and eighth most lethal of all malignancies. Bladder cancer is more common among men than women and among whites than blacks. This is a cancer of older people, as nearly 90% of people with this cancer are over the age of 55. The earlier this cancer is found and treated, the better the outcome. Bladder cancer is a heterogeneous group of tumors with different biologic behaviors. The majority (75-80%) are non-muscle invasive urothelial carcinomas, which frequently recur (>50%), progress to an invasive phenotype in 10-15% of patients, but seldom metastasize. Of all cancers, bladder cancer has the highest cost per patient from diagnosis to death and has the fifth highest cost for total medical care expenditures.

### **Defining disease stage, grade and risk-groups**

The current American Joint Committee on Cancer (AJCC) TNM stage system for bladder tumor classifies papillary lesions according to their degree of invasion in the bladder wall layers. Tumors that are confined to the urothelium or invade only the underlying lamina propria but not the muscularis propria, are generally called non-muscle invasive tumors. These tumors can be classified as carcinoma in situ or Tis (flat lesions, with epithelial abnormalities only), Ta (papillary lesions that do not penetrate the basement membrane) or T1 (tumors that invade only into the lamina propria). These lesions are also classified in a dichotomous fashion according to their degree of dysplasia as low-grade (LG) or high-grade (HG), as defined by the World Health Organization/ International Society of Urological Pathology (WHO/ISUP) 2004 classification. Patients with Tis and/or HG Ta or T1 have an increased risk for recurrence and progression to a muscle invasive cancer. *Recurrence* is defined in this setting as appearance of a tumor in the bladder following the initial treatment, in the same or inferior stage and/or grade, whereas *progression* is defined as recurrence of a tumor of higher stage and/or grade. The other lesions (Ta-1LG) are classified as low- or intermediate-risk for recurrence or progression. This risk stratification is based upon the tumor size ( $\geq 3$ cm vs.  $< 3$ cm), the number of lesions (2 or more, vs. single), and the number of previous recurrences (recurrent vs. primary). Non-invasive bladder tumors in the intermediate-risk category have recurrence rates ranging from 24-38% and 46-62% in 1 and 5 years, respectively. Their rates of progression are about 1% and 6% in 1 and 5 years, respectively. Comparatively, patients in the low-risk category have recurrence in 15% and 31% of cases, but have progression only in 0.2% and 0.8% of the times, at 1 and 5 years, respectively. Therefore, the low/intermediate-risk groups of tumors deserve the attention of this study because the risk of progression, albeit low, is relevant and the recurrence risk is high, even with optimized intravesical chemotherapy.

### **Status of currently available therapies**

There currently are no oral or intravenous therapies for the non-invasive group of bladder tumors. Current treatment strategy is based on surgical transurethral resection (TUR) of the bladder tumor and the application of intravesical chemotherapy. Drugs applied intravesically can be administered in three different regimens:

A) Immediate Post-Operative: Usually a single instillation within the first 6 hours after the TUR.

B) Induction Course: Comprised of a series of 4-6 weekly instillations started within 2-4 weeks after the TUR.

C) Maintenance Course: Usually given in a more delayed and prolonged fashion, usually in a monthly schedule over the period of one year. The maintenance course starts 6 weeks after completion of the induction, between the second and third month after the TUR, and usually includes 10 monthly intravesical instillations.

There is controversy about the ideal regimen and chemotherapy drug to be recommended for each risk group, but for low/intermediate-risk bladder tumors, it is usually offered a single dose of mitomycin-C in the immediate post-operative period, followed by an induction course for 6 weeks using an optimized drug delivery strategy. There may also be a rationale for monthly maintenance single dose intravesical chemotherapy for up to one year after the induction course, i.e. 10 additional monthly intravesical instillations.

A variety of chemotherapeutic agents given by intravesical administration have been used in attempts to reduce the probability of recurrence and progression. The main advantage of this route of administration is the high intravesical concentration achieved, facilitating absorption into the bladder mucosa, with minimal risk of systemic absorption, and thus limitation of the risk of systemic toxicity. Valrubicin, thiotepa, mitomycin-C, doxorubicin, gemcitabine, ethoglucid and teniposide have been used with varying degrees of success for different risk-groups of non-invasive bladder tumors. Long-term recurrence rates are still high despite inclusion of induction and maintenance treatment regimens. Repeat treatments may be effective, yet may be associated with an increased risk of local and systemic side effects and increased costs and bother.

Pharmacologic optimization of intravesical mitomycin-C consists of several procedures that aim at optimization of the urine pH and drug concentration, in order to improve the local effect of the chemotherapy agent when administered intravesically. Although the implementation of the optimized protocol improves the median time to recurrence, the associated tumor-free probability at 5 years remains at 41%.

In summary, there is a need for new therapeutic strategies, using effective and well tolerated drugs that improve overall outcomes while reducing costs, invasiveness, and burden of the disease with minimal toxicity. Chemopreventive treatments are needed in our therapeutic armamentarium, both for maintenance of the initial response to treatment and for the potential for long-term prevention of recurrence and progression. Additionally, there is a need for biomarkers that can be used to predict treatment response before therapy is initiated and also to non-invasively monitor the response during the course of therapy.

### **Estrogen receptors and their biological role**

Estrogen promotes the growth of a number of tissues (e.g. breast and uterine epithelium) and can also stimulate the growth of tumor cells in these tissues. Two ER subtypes, ER $\alpha$  and ER $\beta$ , mediate the physiologic response to estrogen and exhibit separate and overlapping tissue distributions and functions. Unlike in normal and neoplastic breast, where the major effector appears to be ER $\alpha$ , in the urinary tract the predominant receptor is ER $\beta$ , although its biologic role is not completely defined.

### **Rationale for targeting ER**

The finding that ER $\beta$  knock-out mice exhibit increased prostate and bladder hyperplasia suggests a potential role of ER $\beta$  in the development of urologic cancers. While ER $\alpha$  is expressed in 12.4%-18% of bladder cancers, we have found that ER $\beta$  is the predominant receptor expressed in several human bladder cancer cell lines and human bladder cancers comprised in tissue microarrays. An independent report from separate human tissue microarrays, analyzing a heterogeneous group of bladder tumors including different stages and grades from 2 institutions, also confirmed the expression of ER $\beta$  to be higher than ER $\alpha$ , and significantly higher expressed in high-grade/muscle-invasive tumors in comparison with low/non-muscle-invasive tumors. These data suggest that ER may be a rational target for intervention with selective estrogen receptor modulators (SERMs) for treatment and chemoprevention of bladder cancer.

### **Rationale for using SERMs and tamoxifen in bladder cancer**

Tamoxifen, the prototypic SERM, has been utilized for breast cancer treatment for thirty years and more recently for primary and tertiary chemoprevention of breast cancer. Through its interactions with both ER types, it functions as an antagonist in the breast and an agonist in bone and uterus, also reducing circulating cholesterol levels. In breast cancer, the response to tamoxifen generally correlates with ER expression. In addition, ER $\beta$  modifies the action of ER $\alpha$  and reduces the estrogen-like effects of tamoxifen. It is likely that the relative expression levels of the two forms of the ER and its splicing variants will be a key determinant of cellular responses to SERMs with differing agonist and antagonist properties. It is also possible that tamoxifen may modulate ER expression. While tamoxifen has been shown to increase ER $\alpha$  expression in vitro in breast cancer cells, tumors may lose ER expression and become resistant to anti-estrogen therapy. Further evidence of the importance of ER $\beta$  is demonstrated by women with ER $\alpha$  negative breast cancer treated with tamoxifen, showing better survival associated with ER $\beta$  immunoreactivity levels. ER $\beta$  may therefore confer a protective effect in the absence of ER $\alpha$ , retaining sensitivity to therapy using SERMs. The TSU-PR1 bladder cancer cell line, which expresses a high level of ER $\beta$  but not ER $\alpha$ , is sensitive to tamoxifen. Our studies of SERMs in pre-clinical animal models demonstrate that these agents have a potent inhibitory effect on experimental human bladder cancer tumor growth, providing proof of concept of their potential use as therapeutic agents for human bladder cancer. SERMs exert their anti-tumor effects in part via inhibition of proliferation and induction of apoptosis, which correlate with response to treatment. Several urine biomarkers have been shown to correlate with stage and grade of bladder cancer, and the presence or absence of tumor. In addition, persistence of urine biomarker after resection with or without intravesical chemotherapy suggests persistence of occult disease and is frequently associated with a higher risk of subsequent tumor recurrence. Therefore, it is reasonable to expect that if tamoxifen modulates the growth of bladder cancer, this will be reflected by the chosen biomarkers for apoptosis and cell proliferation.

### **Rationale for investigating the role of ER $\beta$ splicing variants in human bladder cancer**

Multiple splicing variants of both ER $\alpha$  and ER $\beta$  have been described in various tissues. The controversy over the function of ER as promoter of carcinogenesis in some tissues and immunomodulator in others may be related to the significant expression of splicing variants. New emerging evidence has suggested that these isoforms are expressed in significant amounts and may be related to different heterogeneous effects obtained by the interaction of these variants forming dimers with the full-length receptors, modulating their action and also binding to

different ligands in the tissues, including estrogens and SERMs. The understanding of the role and mechanisms through which these receptors interact with their ligands is still in its infancy, but knowledge about the wild type (ER $\beta$ 1), and also ER $\beta$ 2 and ER $\beta$ 5, two of the most commonly studied variants, is growing fast. More recent studies in human and animal models of breast and prostate cancer have shown that these splicing variants are expressed more frequently than the wild type in some tissues and that they are not independently functional as homodimers, but they make heterodimers with the wild type ER $\beta$ , thus modulating its activity.

Because our aim #2 is to explore the expression of the human ERs in normal and tumor samples from the bladder, and also their potential modulation after exposure to a SERM drug, these findings will also provide an unique opportunity to report the expression levels of the most common splicing variants in human bladder tissue. Because ER $\beta$  is more common than ER $\alpha$  in the bladder, we will only study the ER $\beta$  splicing variants. Thus, for the purpose of this study, we will evaluate only ER $\alpha$ , and ER $\beta$ 1 (wild type), ER $\beta$ 2 and ER $\beta$ 5.

### **Overall Significance**

Non-invasive bladder cancer is challenging to treat because it is a condition characterized by frequent recurrences that lead to numerous invasive procedures for detection and treatment. The mainstay of therapy for non-muscle invasive bladder cancer, which has remained unchanged for decades, relies on surgical resection (TUR) associated with utilization of intravesical immunotherapy and chemotherapy. Despite our best efforts, these tumors continue to have suboptimal rates of recurrence and require long-term follow-up with costly and invasive procedures. The results of the present study have the potential to improve the oncological outcomes, and at the same time to create a new paradigm in the management of bladder cancer, with the introduction of an oral agent to the current armamentarium. Additionally, with less frequent recurrences and improved biomarkers, this study has the potential to reduce the burden, the costs, and the invasiveness of current treatment and follow-up strategies.

### **Hypotheses:**

Oral tamoxifen treatment will:

- 1) Reduce the size or eliminate small bladder tumor marker lesions, by induction of apoptosis in the tumor cells, being well tolerated with minimum toxicity.
- 2) Show a positive correlation between the clinical response and the pretreatment expression levels of ER (especially ER $\beta$  and its splicing variants) in the tissues.

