### **Specific Aims:**

**Aim 1.** Evaluate the efficacy of tamoxifen for treatment of low/intermediate-risk bladder tumors, assessing for the clinical response of the marker lesion, and analyzing the effects in tissue, in terms of affecting apoptosis and proliferation, while continuously monitoring for treatment toxicity.

**1a.** Evaluate the efficacy of tamoxifen for treatment of low/intermediate-risk bladder tumors, utilizing the RECIST criteria combined with the final biopsy of the marker lesion or the bed of the lesion in case of a complete response. (PRIMARY ENDPOINT)

**1b.** Evaluate the histopathologic effect of tamoxifen treatment in the tumor cells, assessing for the presence of necrosis, fibrosis, apoptosis and scar tissue.

**1c.** Evaluate the treatment effect in the histologic markers for apoptosis (TUNEL) and proliferation (Ki-67).

**1d.** Monitor treatment toxicity.

**Aim 2.** Evaluate the expression levels of ER $\alpha$  and ER $\beta$  (including splicing variants) before and after treatment with tamoxifen, in both normal and tumor tissues, and correlate the clinical response with the expression levels of these ERs.

**2a.** Report on and compare the pre and post-treatment expression levels of ER $\alpha$  and ER $\beta$  (including their splicing variants, more specifically ER $\beta$ -1, ER $\beta$ -2 and ER $\beta$ -5) in both normal and tumor tissues.

**2b.** Correlate the observed clinical effect, measured by the proportion of subjects that had complete or partial responses, with the pretreatment expression levels of ERs in tumor tissue.

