### **Overall study description**

Patients with primary or recurrent low/intermediate-risk papillary urothelial carcinoma of the bladder will undergo resection of all but one marker lesion, measuring at least 6mm but no greater than 10mm, and biopsy of normal-appearing mucosa. Patients with a solitary tumor will undergo only biopsy prior to treatment. A 2mm cold cup biopsy of the marker lesion will always be performed to rule out a potential high-grade lesion and for assessment of pretreatment immunohistochemistry expression levels of ER $\alpha$ , ER $\beta$ 1, Ki-67 (proliferation marker) and TUNEL (apoptosis marker). If there are multiple tumors, all lesions, except the marker lesion will be resected and sent for analysis. These patients will not receive single immediate post-operative intravesical instillation of mitomycin-C. They will then undergo a 12-week course of treatment with tamoxifen administered as a single daily oral dose of 20mg. At the completion of therapy, patients will undergo resection of the marker lesion (or biopsy of the tumor bed, if a complete response is observed) and biopsy of normal-appearing bladder mucosa again. Toxicity evaluations will be performed at the beginning (day 3), midway (week 6), and at completion of treatment (week 12), prior to resection of the marker lesion. A final assessment for toxicity will also be performed 30 days after completion of therapy as well as a second definitive resection of the marker lesion. Urine samples will be obtained with the index tumor in place (marker lesion), and after completion of treatment, at the time of definitive transurethral resection of the index tumor, as part of the standard clinical care of these patients, and at the discretion of the surgeon for assessment of urinary cytology. The urine samples will not be utilized for the research study. All normal-appearing bladder biopsies (pre and post-treatment), the additional tumors (in case of multiple lesions), and the definitive resection of the marker lesion (in the absence of response to therapy) will provide sufficient material for immunohistochemistry assessment of the expression levels of ER $\alpha$ , ER $\beta$ -1, ER $\beta$ -2, ER $\beta$ -5, Ki-67, and TUNEL, and also for RT-qPCR for mRNA analyses of ER $\alpha$ , ER $\beta$ -1, ER $\beta$ -2, and ER $\beta$ -5. The pretreatment biopsy of the marker lesion will be performed with a smaller biopsy forceps and will provide limited material, sufficient only for immunohistochemistry assessment of the expression levels of ER $\alpha$ , ER $\beta$ -1, Ki-67, and TUNEL.

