### Office visit on 2nd Resection only occurs if patient had a single Tumor during 1st Resection. All patients with Multiple tumors at 1st Resection will have 2nd Resection in an outpatient hospital setting.

#### Completed per PI description

## **Procedures:**

**Aim 1 Procedures:** Transurethral resection of bladder tumors is a well-defined surgical technique used for diagnosis, staging, and treatment of bladder tumors of different stages. Briefly, patients undergo general anesthesia. Under proper aseptic technique, an optical resectoscope with video imaging capabilities is introduced into the bladder retrogradely via the urethra. The bladder tumor is resected using a resection loop connected to an electric source. The technique involves scooping movements of the loop, while cauterization is applied, to allow concomitant tissue cut and hemostasis. Measurement of the lesions will be performed by comparison with the standardized size of the resection loop.

Collection of samples: Biopsies of the marker lesion and normal appearing mucosa located remotely from the marker lesion will be processed using standard procedures for formalin fixation and paraffin embedding. These tissues will be tested by immunohistochemistry for Ki-67 and TUNEL. Each specimen will also be stained with hematoxylin and eosin to verify urothelial carcinoma histology.

**Aim 2 Procedures:** Collection of samples: Biopsies of the marker lesion and normal mucosa remote from the marker lesion will be processed using standard procedures for formalin fixation and paraffin embedding. The pretreatment biopsy of the marker lesion will be performed with a 2mm cold-cup biopsy forceps, to avoid affecting the histologic characteristics of the marker lesion. Because of the limited amount of tissue yield in this biopsy, we will only perform immunohistochemistry analyzing Ki-67, TUNEL, ER $\alpha$  and ER $\beta$ -1. The normal bladder biopsies, the resection of additional tumors synchronous to the marker lesion (in case of multiple lesions), and the final definitive resection of the marker lesion will be performed with a regular rigid biopsy forceps or resection loop, yielding much larger specimen fragments. These tissues will be tested by immunohistochemistry and RT-qPCR for the mRNA of ER $\alpha$ , ER $\beta$ -1, ER $\beta$ -2 and ER $\beta$ -5. Each specimen will also be stained with hematoxylin and eosin to verify urothelial carcinoma histology.

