**Specific Aim 2a and 2b:** All data will be presented and summarized using descriptive statistics. The percentage of positive cells with nuclear immunoreactivity is recorded on a semi-quantitative scale: results are categorized as negative (< 10% cell labeling) or positive ( $\geq$  10% cell labeling). Normal breast tissue and transfected cells with known ER will be used as positive control and normal tissues such as liver and spleen, as well as cells transfected with empty vectors will be used as negative controls.

We will correlate pretreatment ER levels with the proportion of the positive response (composite endpoint of clinical PR and CR, and a final biopsy) of the marker lesion to determine associations with treatment effect. Specifically, Pearson's or Spearman's correlation coefficients will be calculated to estimate and test for significant correlations between the expression level of the ERs and the primary endpoint. Comparison of ERs expression levels from normal and bladder tumor tissues measured prior to treatment will also be performed using independent sample tests as described above. Non-parametric tests will be utilized as appropriate.

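### Hypothesis 2 (ER expression predicts response) has no designated deciding ER measure: with 10 to 18 candidates and no multiplicity rule, a false positive correlation has roughly a 9-37% chance, against 2.5% for one named test.

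*Combined protocol and SAP*

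**What the plan says.** Under Hypotheses, item 2 predicts that treatment will "Show a positive correlation between the clinical response and the pretreatment expression levels of ER", with emphasis on ERβ and its splicing variants, in the tissues generally. Under Specific Aims, Aim 2b relates response to ER more narrowly, "with the pretreatment expression levels of ERs in tumor tissue".

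The paragraph on Specific Aims 2a and 2b, in the statistical considerations for the secondary aims, says: "We will correlate pretreatment ER levels with the proportion of the positive response". It adds that "Pearson's or Spearman's correlation coefficients will be calculated to estimate and test for significant correlations" with the primary endpoint. It names no tissue, receptor or assay for that correlation. For ER immunoreactivity it says "results are categorized as negative (< 10% cell labeling) or positive" (10% or more), although the correlation is described as using the expression level.

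The measures available before treatment follow from Overall study description and Procedures (Aim 2):

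- The marker-lesion biopsy "will provide limited material, sufficient only for immunohistochemistry assessment of the expression levels of ER"α and ERβ-1, plus Ki-67 and TUNEL.
- For the normal-mucosa biopsies and the synchronous tumours of patients with multiple lesions: "These tissues will be tested by immunohistochemistry and RT-qPCR for the mRNA of ER"α, ERβ-1, ERβ-2 and ERβ-5.

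**The concern.** A directional hypothesis is to be tested for significance, but several choices that determine the result are left open: tissue, receptor, assay, scale and coefficient. Any one positive correlation among the candidates could be reported as support for Hypothesis 2.

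Reading on does not settle the matter. The hypothesis stresses the splicing variants, yet ERβ-2 and ERβ-5 are not measured before treatment in the lesion whose response is scored. They exist at that time only in normal mucosa, which Aim 2b leaves out, or in synchronous tumours, which patients with a solitary tumour do not have.

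At stake is how far a reported ER-response association can be believed. The background states a need for markers that predict response before therapy, and the Benefits section says the study will inform the design of further phase II and III trials.

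**Working it through.** **Sample size frame.** The plan gives no alpha, power or multiplicity figure for the ER correlations, so only the sample size can be reproduced. The Simon design (0 of 9, then 2 or fewer of 17; P0 = 0.05, P1 = 0.30) has exact rejection probability Σ b(x₁; 9, p) · P(X₂ ≥ 3 − x₁), summed over x₁ = 1 to 9 with X₂ ~ Bin(8, p). This is 0.0466 at P0 and 0.9045 at P1, in line with the stated 0.05 and 0.90. Then 17 / 0.90 = 18.9, giving the stated 19. So n = 17 is used below.

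**Count of pretreatment ER measures.**

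- Marker lesion: 2 receptors × IHC = 2, in every patient.
- Synchronous tumours: 4 receptors × 2 assays = 8, in multifocal patients only.
- Normal mucosa: 4 × 2 = 8.
- Tumour tissue: 2 + 8 = 10. All tissues: 10 + 8 = 18.

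**False support with independent tests.** Assume two-sided 5% per test. Only a positive correlation supports Hypothesis 2, so each test contributes 2.5%, and the chance of at least one is 1 − 0.975^k:

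| k | Positive direction | Either direction, 1 − 0.95^k |
|---|---|---|
| 1 | 2.5% | 5% |
| 2 | 4.9% | 9.8% |
| 10 | 22.4% | 40.1% |
| 18 | 36.6% | 60.3% |

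**Simulation with n = 17 and no true association, positive direction** (response rate 30%, or 3 or 5 responders fixed):

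- Continuous measures in all patients, one coefficient, between-measure correlation 0 to 0.5: about 15-22% (k = 10) and 21-37% (k = 18).
- IHC cut at 10%, qPCR continuous, half the patients multifocal, IHC positivity 50% to 80%, correlation 0 or 0.5: about 9-19% and 16-33%.

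Together these give the 9-22% and 16-37% in the heading. They are not bounds:

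- At between-measure correlation 0.8 (continuous, one coefficient) the rates fall to about 9% and 12%.
- With IHC cut at 10%, positivity of only 15%, 3 responders and independent measures in all patients, they rise to about 36% and 55%.

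**Open choice of coefficient.** If Pearson or Spearman may be picked afterwards and all measures are continuous, independence gives about 26-27% and 42-44%; correlation 0.5 gives about 17-18% and 24-25%. For IHC cut at 10%, both variables are binary and the two coefficients coincide, so the choice matters only for qPCR (4 of 10 measures, or 8 of 18).

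**Sensitivity of one named test.** By Fisher's z, 80% power at n = 17 needs a true r of tanh[(1.96 + 0.84)/√14] ≈ 0.63.

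**The case against.** The strongest reply is that this is a secondary, partly exploratory aim in a small phase II trial. Only Aim 1a is marked as the primary endpoint, the only formal null hypothesis is that of the Simon design, and the rationale for the splicing variants describes Aim 2 as exploring ER expression. That lowers the weight of the point but does not answer it: the directional hypothesis and the commitment to significance testing both stand, and nothing labels the ER-response test exploratory.

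The reply is right about four stronger readings that a reader might infer:

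- *No test is designated at all.* The analysis section does name the outcome (the composite response) and a family of coefficients. The deciding ER measure is what is missing.
- *All 18 measures compete.* Aim 2b restricts the correlation to tumour tissue, so 18 is a ceiling that rests on the looser wording of Hypothesis 2 and the analysis paragraph. Only 2 measures come from every patient's marker lesion.
- *The tests run at an unadjusted 5%.* The 0.05 level is stated for the Ki-67 and TUNEL paired t-tests. For the ER correlations it is an assumption.
- *The result will be used to select patients for later trials.* The documents do not say so.

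**Conclusion.** The point holds: Hypothesis 2 has no deciding ER measure, scale, alpha or multiplicity rule, and the stated emphasis on splicing variants does not match what is measured in the marker lesion before treatment. The chance of at least one false positive correlation is about 9-22% with 10 measures and 16-37% with 18, against about 2.5% for one named test.

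These ranges rest on assumptions that the documents do not supply: 5% two-sided per test, the response rate, the correlation between measures, IHC positivity and the share of multifocal patients.

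A reader might conclude that false support is likely. That does not follow. In the direction the hypothesis predicts, the rate exceeds one half only in an extreme corner (18 independent measures, 15% positivity, 3 responders). The 40% and 60% figures count negative correlations, which contradict the hypothesis.

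The primary endpoint is not affected.

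**What to change.** In Hypotheses (item 2), Aim 2b and the Specific Aim 2a and 2b analysis paragraph, name one deciding test:

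- **Measure:** pretreatment ERβ-1 by immunohistochemistry in the marker-lesion biopsy. It is the only ERβ form measured there before treatment.
- **Scale:** continuous percent positive nuclei, as the plan already does for Ki-67 and TUNEL, and not the 10% cut. Under the cut, a Spearman test is a 2×2 comparison, undefined if every lesion is positive.
- **Test:** Spearman correlation with the composite response, two-sided 5%.

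Report every other ER measure as an exploratory estimate with a confidence interval, with a Holm correction across that family if p-values are claimed. Align the tissue wording of Hypothesis 2 with the tumour tissue of Aim 2b. Declaring Hypothesis 2 exploratory throughout, without significance claims, would also close the gap.

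The cost is wording in three places and no new specimens; the laboratory must record the percentage and not only the category. The downside is that signals in ERα, ERβ-2, ERβ-5 or mRNA, including the splicing variants that the hypothesis stresses, become hypothesis-generating only.
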